9.10.4. Other Secondary Endpoints

9.10.4.1. Objective Response Rate per RECIST v1.1

Objective response rate per RECIST v 1.1 over the entire study, defined as the number of participants with a BOR of CR or PR at any time on study, and its corresponding 95% CI will be presented.

The best overall response (BOR) up to a specific timepoint for an individual participant will be determined as follows:

- Complete response (CR): at least one CR result before any Progressive Disease result, up to and including the specific timepoint of interest
- Partial response (PR): at least one PR result before any Progressive Disease result (and not qualifying for a CR), up to and including the specific timepoint of interest
- Stable disease (SD): at least one SD before any Progressive Disease result (and not qualifying for a CR or PR), up to and including the specific timepoint of interest
- Progressive disease: a result of Progressive Disease up to and including the specific timepoint of interest, not preceded by any result of CR, PR or SD
- Not Evaluable (NE): not meeting the above definitions, and no Progressive Disease before the specific timepoint of interest and the specific timepoint of interest assessment is NE or missing

The primary analysis of BOR will be conducted based on RECIST v1.1 based on IRR. Supportive analyses based on TVS and mRECIST from IRR and based on investigator assessment per RECIST v1.1 will be provided.

9.10.4.2. Tumor Response per mRECIST

Objective response rate by mRECIST at Week 25 will be compared between 2 treatment groups using a two-sided Cochran-Mantel-Haenszel test stratified by the randomization stratification factors at the 0.05 alpha level based on the ITT Set. The 95% CI in each arm and the difference, along with its 95% CI, will be presented. Although it is not part of the hierarchical testing, the analysis will use the same method used for the primary endpoint analysis. The tumor response status at Week 25 based on mRECIST will follow the same approach described in Table 2 for the primary endpoint. The criteria for mRECIST is identical to RECIST v1.1, except that measurements are taken along the short-axis dimension perpendicular to the longest dimension and ideally also to a reproducible adjacent landmark, such as the femoral bone or a tendon.

All tumor response per mRECIST data will be presented in by-participant listings.

9.10.4.3. Duration of Response

Duration of response (DOR) is defined as the time from the first documented objective response (CR or PR) until the time of disease progression or death by any cause, whichever occurs earlier. DOR will be summarized in two sets of participants, firstly for participants with an objective response at Week 25 and secondly for those who achieved CR or PR as BOR on study to the study treatment in the ITT Set. DOR in weeks is calculated as

• (Earlier of Date of Progressive disease or death, or censoring – date of first response + 1) / 7

Participants will be censored according to following rules:

• For participants who undergo surgical resection of target or non-target lesions, or have received anti-tumor treatments other than the study treatment before documented date of the first disease progression, DOR will be censored at the date of the latest evaluable progression-free radiologic assessment prior to start date of the anti-tumor therapy.

- For participants who have not progressed nor died, DOR will be censored at the last evaluable radiologic assessment.
- For participants who have first disease progression or die after two or more consecutive missed/non-evaluable assessments, DOR will be censored at the time of the evaluable radiologic assessment immediately prior to the two or more consecutive missed/non-evaluable radiologic assessments.

DOR will be summarized for responders in each of the following three groups:

- 1. DOR in vimseltinib arm: Participants randomized to receive vimseltinib in Part 1 using data from Part 1 and Part 2 (including extension period);
- 2. DOR in placebo arm: Participants randomized to receive placebo in Part 1, using all available data until initial dose of vimseltinib in Part 2;
- 3. DOR after crossover to vimseltinib: Participants randomized to receive placebo in Part 1 and crossed over to vimseltinib in Part 2.

For Group (1), tumor assessment data from both Part 1 and Part 2 (including extension period) will be combined, and the baseline assessment will be the one recorded during the Screening period. Censoring for Group (1) will follow the rules listed above. For Group (2), the duration of response will be censored based on the rules listed above with vimseltinib being considered as another anti-tumor treatment, and with the screening assessment serving as baseline. For Group (3), the tumor assessment data in Part 2 (including extension period) will be used, with the baseline assessment being the last one before the first dose of vimseltinib in Part 2. Censoring for Group (3) will follow the rules listed above.

DOR time will be summarized via Kaplan-Meier (KM) methodology including the total number and percentage of participants with events and by type of event (disease progression or death), total number and percentage of censored participants and by censoring reason, the DOR percentiles (25th, 50th [median], and 75th), DOR probabilities at pre-specified timepoints (e.g., 25 weeks and 49 weeks if applicable) with associated 2-sided 95% confidence intervals, and KM plot of the estimated survival functions for DOR.

Duration of response will also be summarized for Groups (1) and (3) combined, reflecting all responses observed while receiving vimseltinib.

KM plots will be provided to graphically present the DOR by group.

The analysis described above for DOR for those participants with an objective response at Week 25 will be performed separately based on RECIST v1.1 and TVS per IRR.

The analysis described above for DOR for those who achieved CR or PR as BOR on study will be performed separately based on RECIST v1.1, TVS, and mRECIST data. Duration of response data will be presented in a listing.

9.10.5. Sub-group Analyses

The primary efficacy endpoint and key secondary efficacy endpoints will be analyzed in participant subgroups defined as follows:

• Tumor location (lower limb vs all other)

- Region (U.S. vs non-U.S.)
- Participants with disease located in large joints (shoulder, elbow, hip, or knee) vs small joints (joints other than the shoulder, elbow, hip, or knee)
- Participants with disease located in the knee
- Disease subtype (localized vs diffuse)
- Participants at sites in the EU region only
- Age $(18 \le age < 50, 50 \le age < 65, age \ge 65)$
- Gender (female vs male)
- Prior surgery (yes vs no)
- Prior imatinib/nilotinib (yes vs no)

The applicable key secondary efficacy endpoints are TVS, ROM, PROMIS-PF, worst stiffness NRS, EQ-VAS and BPI-30 response.

9.10.6. Sensitivity Analyses for Missing Data

The preponderance of missing data for the key secondary efficacy endpoints of Active ROM, PROMIS-PF, Worst Stiffness NRS, and EQ-VAS will be evaluated. If there is more than 10% of missing data at Week 25 in any of the endpoints, then the impact of the missing data will be explored for that endpoint and will include, but may not be limited to, the following analyses:

- Multiple imputation based on randomized treatment to mimic missing at random
- A Pattern Mixture Model approach where participants who discontinued treatment due to an adverse event on vimseltinib will be imputed based on the missing not at random assumption and be imputed as if they received placebo.

In any exploration of missing data impact where a seed is required, the seed will be set to 20230428.

9.10.7. Exploratory Efficacy Analysis (Part 1 & 2)

There will be no formal testing for exploratory endpoints, descriptive statistics will be presented and nominal p-values may be provided.

As will be done for safety analyses, exploratory efficacy endpoints presented over time will be summarized following two different approaches. The first approach will be limited to data from Part 1 and will focus on comparisons between participants who received vimseltinib versus participants who received placebo during this period. The second approach will combine data from both Part 1 and Part 2 (including extension period) and will focus on the observations and assessments while participants are receiving vimseltinib. Therefore, in this second approach, participants randomized to Placebo in Part 1, will have as their reference day the first dose date of vimseltinib which will occur in Part 2, and their data from Part 1 while receiving placebo will be excluded.

For observed value and change from baseline analyses, summary statistics at each scheduled visit will be presented.

9.10.7.1. Objective Response Rate at Specific Timepoints

Response at a specific timepoint will be derived based on reported overall tumor responses at different evaluation timepoints from the date of first dose up to and including the specific timepoint assessment. Response at Week 25 will be determined based on Section 9.10.2 and responses at other timepoints will be determined based on:

- Complete response (CR): at least one CR reported up to and including the specific timepoint assessment and the specific timepoint assessment is not Progressive Disease or NE
- Partial response (PR): at least one PR but no CR reported up to and including the specific timepoint assessment and the specific timepoint assessment is not Progressive Disease or NE
- Stable disease (SD): at least one SD but no CR nor PR reported up to and including the specific timepoint assessment and the specific timepoint assessment is not Progressive Disease or NE
- Progressive disease: Progressive Disease at the specific timepoint assessment or Progressive Disease before the specific timepoint regardless of response status at the specific timepoint
- Not Evaluable (NE): no Progressive Disease before the specific timepoint and the specific timepoint assessment is NE or missing

ORR at Week 25, 49 or 73 is defined as the proportion of participants with Response at the specific time point being either CR or PR. The denominator for will include all participants in the ITT Set who have reached the Week 25, 49 or 73 timepoint or have discontinued from treatment or the study prior to that timepoint. An exact 95% confidence interval (CI) on the rates of response will also be presented.

These exploratory analyses will be conducted based on RECIST v1.1, TVS and mRECIST from IRR, and based on investigator assessment per RECIST v1.1.

Swimlane plots will present objective response and time to response duration for individual participants where time to response is defined as date of first CR or PR - treatment start date + 1.

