8.3. Analysis Visit Window

For by-visit (or cycle) statistical summaries, data will be analyzed according to the scheduled visit assigned on the eCRF (also referred to as the nominal visit). Otherwise, data collected as unscheduled assessments will be mapped to a scheduled visit using a visit window from Cycle 1 Day 1. The visit window for a specific visit of interest will go from the midpoint between the preceding visit and the visit of interest to the midpoint between the visit of interest and the subsequent scheduled visit.

For PRO, cycles will be mapped based on the expected length of 28 days to determine where assessments will be assigned based on the participant's Day 1 of each cycle.

If there are more than one unscheduled result, visit date will be used to calculate study day and the valid assessment within the visit window closest to the target study day will be used. If two or more assessments are the same distance apart from the target study day, then the earliest assessment will be used. The early termination visit may also be mapped to a derived visit window. Data that are collected from unscheduled visits and cannot be mapped to a scheduled visit will not be included in the by-visit summary tables but will be presented in the listings.

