9.1. General Methods

Data collected in this study will be documented using summary tables and participant data listings. Continuous variables will be summarized using descriptive statistics (number of observations, mean, median, standard deviation, minimum, and maximum). Categorical variables will be summarized using frequencies and proportions. Time-to-event data will be summarized via Kaplan-Meier (KM) methodology using the 25th, 50th (median), and 75th percentiles with associated 2-sided 95% confidence intervals (CIs).

Medical history, AEs, and concurrent procedures will be coded using Medical Dictionary for Regulatory Activities (MedDRA) version 26.0 (or higher). Prior and concomitant medications will be coded using the World Health Organization (WHO) Drug Dictionary March 2023 Global B3 or later.

This study comprises 2 periods: the randomized double-blinded period (Part 1) and the open-label portion that occurs after unblinding the study treatment at Week 25 (or earlier if there is a treatment discontinuation due to a centrally confirmed disease progression) (Part 2).

Unless otherwise specified, the ITT and PP Sets are used for efficacy analysis and the SAF is used for the safety analysis.

The primary analysis will be conducted at the earliest when all participants have completed the double blinded treatment period (Part 1).

In general, unless otherwise specified, data summaries will be presented by treatment group (vimseltinib versus placebo) and overall. Between-group comparisons will focus on the comparative performance of vimseltinib versus placebo. All statistical tests will be conducted at a 2-sided significance level of 0.05.

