9.10.7.2. Clinical Benefit Rate

Clinical benefit rate (CBR) is defined as the proportion of participants who have a response (CR or PR) or stable disease (SD). CBR will be tabulated at Week 25, 49, and 73. CBR will be calculated among participants in the ITT Set. The denominator will include all participants in the ITT Set who have reached the Week 25, 49 or 73 timepoint or have discontinued from the study prior to that timepoint.

Clinical benefit at Week 25, 49 or 73 will be derived based on reported overall tumor responses at different evaluation timepoints from the date of first dose up to and including the Week 25, 49 or 73 timepoint.

Clinical benefit status at Week 25, 49, or 73:

• Clinical Benefit (CB):

- at least 1 CR or PR result, up to and including the specific timepoint of interest
- only SD or NE results obtained up to the specific timepoint of interest and a SD result at the specific timepoint of interest
- No Clinical Benefit (NCB): Not meeting the above definition for CB

These exploratory analyses will be conducted based on RECIST v1.1, TVS and mRECIST from IRR, and based on investigator assessment per RECIST v1.1.

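### At a data cut before everyone is due, the exploratory Week 49 and 73 response rates count not-yet-due participants only if they have discontinued, so the rates are biased low

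*SAP*

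**What the plan says.** **Response rate, SAP 9.10.7.1.** The denominator is ITT participants "who have reached the Week 25, 49 or 73 timepoint or have discontinued from treatment or the study prior to that timepoint". CR or PR at the timepoint requires that "the specific timepoint assessment is not Progressive Disease or NE". A participant is NE if there is "no Progressive Disease before the specific timepoint and the specific timepoint assessment is NE or missing", even after an earlier PR. Exact 95% intervals are attached, and the rule serves RECIST v1.1, TVS, mRECIST and the investigator reads.

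**Clinical benefit rate (CBR), SAP 9.10.7.2.** The denominator is ITT participants "who have reached the Week 25, 49 or 73 timepoint or have discontinued from the study prior to that timepoint"; stopping treatment alone does not qualify. The numerator accepts "at least 1 CR or PR result, up to and including the specific timepoint of interest", so an earlier response is enough.

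**Timing of the cut, SAP 9.1.** "The primary analysis will be conducted at the earliest when all participants have completed the double blinded treatment period (Part 1". No analysis is scheduled for when all participants are past Week 49 or 73.

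**Crossover participants, SAP 9.10.7.** In the second approach, "participants randomized to Placebo in Part 1, will have as their reference day the first dose date of vimseltinib".

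**Windowing, SAP 8.3.** "The early termination visit may also be mapped to a derived visit window".

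**Status.** Protocol 6.2 and SAP 4.4 list ORR at Week 49 as exploratory. They list neither ORR at Week 73 nor CBR. SAP 9.10.7 rules out formal testing of exploratory endpoints.

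**The concern.** Take a participant first dosed 35 weeks before the cut. Week 49 has not come due. If the participant is still on vimseltinib and in PR, the rule leaves them out. If they have stopped treatment, the rule brings them in, and with no Week 49 scan they are NE or PD. Among recent enrollees, entry to the denominator therefore depends on failing.

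The effect grows with the share of participants not yet due, so it is larger at Week 73 than at Week 49. A table of Weeks 25, 49 and 73 from one early cut could look like fading response when none has been lost, and the rates would drift upward at later cuts as more participants come due. An exact interval does not correct this.

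The second problem is the different discontinuation rule for CBR. Protocol 11.8 follows most participants who stop treatment for up to 2 years. Someone not yet due who is off drug but still in the study counts in ORR and not in CBR. The SAP gives no reason for the difference.

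**Working it through.** The documents state no figure for ORR at Week 49 or 73. Their one related figure, 98% power for 35% versus 5% with 80 and 40 participants (SAP 5), reproduces at 98.3% by exact enumeration of the two-sided Fisher test. It concerns the primary endpoint and is not affected.

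**From the documents:** 80 vimseltinib participants (SAP 5); 24 weeks of Part 1, so the earliest cut falls about F = 24 weeks after the last randomization (SAP 2 and 9.1).

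**Assumed, not in the documents:** uniform accrual over A = 52 or 78 weeks; constant discontinuation hazard giving d = 5%, 10% or 15% by 24 weeks; true rate p = 35% at each week, with discontinuers counted as non-responders. SAP 5 gives 35% for the primary endpoint and 15% dropout with no time frame; both are borrowed only as illustrations.

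**Formulas.** Let T = 48 or 72 weeks from first dose to Week 49 or 73.
- Due = 80 × (A + F − T)/A. The remaining participants have follow-up spread evenly between F and T.
- λ = −ln(1 − d)/24.
- Added = (80 − due) × {1 − [exp(−λF) − exp(−λT)]/[λ(T − F)]}.
- Reported rate = p × due/(due + added).

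**Worked case, Week 49, A = 52, d = 10%.** Due = 80 × 28/52 = 43.1, which leaves 36.9 not due. With 24λ = 0.1054, the discontinued share is 1 − (0.90 − 0.81)/0.1054 = 0.146, so added = 5.4 and left out = 31.5. Reported = 0.35 × 43.1/48.5 = 31.1%.

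| Week | Accrual (weeks) | Due, of 80 | Added at d = 5/10/15% | Left out, still on drug | Reported, true 35% |
|---|---|---|---|---|---|
| 49 | 52 | 43.1 | 2.7 / 5.4 / 8.0 | 34.2 / 31.5 / 29.0 | 32.9 / 31.1 / 29.5% |
| 49 | 78 | 55.4 | 1.8 / 3.6 / 5.3 | 22.8 / 21.0 / 19.3 | 33.9 / 32.9 / 31.9% |
| 73 | 78 | 30.8 | 4.8 / 9.3 / 13.5 | 44.4 / 39.9 / 35.7 | 30.3 / 26.9 / 24.3% |

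In whole numbers: 14 responders among 40 due is 35.0%; adding 6 not-yet-due discontinuers gives 14/46 = 30.4%.

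**Checks.** The ratio of reported to true rate is due/(due + added), which does not depend on p. If nobody is short of the timepoint, added = 0 and the reported rate equals p. For Week 25 in the randomized arms, everyone is due at the earliest permitted cut, so there is no bias. Crossover participants, timed from their first vimseltinib dose, may not be due even for Week 25 in the second approach.

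**CBR.** A not-yet-due study discontinuer counts as benefit if there was an earlier CR or PR, and as no benefit otherwise. The direction therefore depends on how often that group had responded compared with the benefit rate among those due. The documents do not settle it.

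**The case against.** **It is conditional.** SAP 9.1 gives an earliest trigger, not a statement that Weeks 49 and 73 will be interpreted at that cut. This stands: a reader might infer that the rates are biased at any cut, and they are not.

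**Little rests on it.** The analyses are exploratory and the error runs against the drug. Longer-term efficacy is also shown by two secondary endpoints, ORR over the whole study (SAP 9.10.4.1) and duration of response by Kaplan-Meier with censoring (SAP 9.10.4.3). This stands and limits the severity. It also shows that the SAP already allows for incomplete follow-up elsewhere.

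**The size is uncertain.** At 5% discontinuation the Week 49 loss is 1 to 2 points. It would be tempting to read the 15% as dropout by Week 25, but SAP 5 gives no time frame and does not call it treatment discontinuation. It would also be tempting to headline shorter accrual. Week 49 with 26-week accrual reads 19/13/10%, and Week 73 with 52-week accrual 16/11/8%. In both, only about 6 of 80 are due (80 × 2/26 and 80 × 4/52), too few for a useful estimate under any rule. Holding p at 35% also implies a rising rate among those retained: at d = 10%, 0.35/0.81 = 43% at Week 49 and 0.35/0.729 = 48% at Week 73.

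**A discontinuer may have a usable scan.** An end-of-treatment scan mapped into the window under SAP 8.3 could make an occasional not-yet-due discontinuer a responder. Hence almost always, not always.

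**The ORR and CBR denominators may coincide later.** If reaching the week means still being in the study then, off-drug participants enter CBR as they pass it, and at maturity the denominators agree. If it means being on treatment, they may not. The SAP does not say which.

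**Conclusion.** The concern holds for ORR at Weeks 49 and 73 at any cut where some participants have not had time to reach the week. The SAP permits such a cut and names no later one. The direction for ORR is downward, apart from the rare windowed scan. On the stated assumptions the loss from a true 35% is about 2 to 6 points at Week 49 with 52-week accrual, 1 to 3 points with 78-week accrual, and 5 to 11 points at Week 73 with 78-week accrual. It is zero once all participants are past the timepoint.

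A reader might also infer that the main result is affected or that CBR is biased low too. The documents support neither. The primary analysis keeps the full ITT Set and counts a missing Week 25 scan as non-response (SAP 9.10.2), so it and the testing hierarchy are untouched. For CBR, an earlier response counts as benefit, so the direction is open; what holds is that at an early cut CBR and ORR can rest on different people. This is worth correcting in the SAP but does not threaten the trial's conclusions.

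**What to change.** In both SAP 9.10.7.1 and 9.10.7.2, define the denominator as all ITT participants whose Week 25, 49 or 73 target date, plus the upper bound of the Section 8.3 analysis window, falls on or before the data cut-off, regardless of treatment or study discontinuation. Count the date from first dose; from randomization for those never dosed, so that the ITT Set stays whole; and from first vimseltinib dose for crossover participants in the second approach.

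Leave both numerators alone. For ORR, due participants without an evaluable timepoint scan remain non-responders under 9.10.7.1. For CBR, an earlier CR or PR still counts under 9.10.7.2, so a blanket instruction to score such participants as failures would contradict that section.

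The cost is a short edit to each section, and a smaller denominator with a wider interval at an early cut. For Week 49 the next scheduled visit is Week 61 (protocol Table 3), so the window closes at (49 + 61)/2 = Week 55, or 54 weeks after first dose. With 52-week accrual, 80 × (52 + 24 − 54)/52 = 33.8 participants would qualify, against 48.5 in the worked case. The approximate 95% half-width is 1.96 × √(0.35 × 0.65/33.8) = 16 points, against 1.96 × √(0.311 × 0.689/48.5) = 13 points for the biased rate. The interval is wider, but it is centered on the right value.
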